### **2.5.2 Blinding**

Not applicable; this is an open-label study.

## **3 DATA CONSIDERATIONS**

### **3.1 Protocol Deviations**

A deviation occurs when site personnel or a participant does not adhere to the protocol's stipulated requirements, whether inadvertently or planned. All identified protocol deviations will be documented (entered in the CRO's Clinical Trial Management System or equivalent), classified, and reviewed on an ongoing basis through out the study according to procedures outlined in the Protocol Deviations Management Plan (PDMP). The final protocol deviation data will be reviewed and locked prior to database lock and incorporated into Study Data Tabulation Model (SDTM).

### **3.2 Analysis Populations**

There will be four analysis populations for this study:

The Intent-to-treat (ITT) Population will include all participants who are randomized. Participant disposition and baseline demographics will be summarized by IP group (Group 1, 2, and 3) and overall for the ITT population according to the group which the participant is randomized to.

The Safety Population will include all randomized participants who receive at least one dose of either antibiotic or AV7909. Participants will be included in the IP group (Group 1, 2, and 3) according to the treatment they received.

The PK Population will include all participants in Group 1A and Group 2A who:

- Received two doses of AV7909 according to the protocol (e.g., correct dose, no temperature excursion, and within the study-specified windows).
- If in Group 1A, received at least 5 of the 7 in-clinic ciprofloxacin doses between Day 4 through the morning of Day 8 and between Day 31 through the morning of Day

35; or if in Group 2A, received at least 7 of the 9 in-clinic doxycycline doses between Day 2 through the morning of Day 8 and between Day 32 through the morning of Day 38.

- Have adequate data for calculation of the PK parameters ( $AUC_{0-12h}$  and  $C_{max}$ ) at the Day 8 (both Group 1A and 2A) and Day 35 (Group 1A) or Day 38 (Group 2A) visits.
- Have no protocol deviations/events that would affect ciprofloxacin or doxycycline steady state PK assessment or immunogenicity results.

Exclusion of participants from population will be done on a case-by-case basis at the time of the PK parameter analysis.

The PK Population will be used for all PK analyses. Participants will be included in the treatment group (Group 1A or Group 2A) according to the antibiotic received.

The Immunogenicity Population will include all randomized participants who:

- Received two doses of AV7909 according to the protocol (e.g., correct dose, no temperature excursion, and within the study-specified windows).
- Had a valid immunogenicity (TNA) result at Day 1 (pre-vaccination) with no evidence of previous exposure to anthrax or an anthrax vaccine (i.e., TNA below the limit of detection of 0.059).
- Had a valid immunogenicity (TNA) result at Day 37, within the study-specified window.
- Participants in Group 1 or Group 2 should have taken at least 50% of the protocol-specified antibiotic doses.

The Immunogenicity Population will be used for the immunogenicity analyses. Participants will be included in the IP group (Group 1, 2, and 3) according to the treatment they received.

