6.1.4. Administration of AV7909

AV7909 will be administered to all participants in all groups as a 0.5 mL IM vaccination in alternate arms on Days 8 and 23. Vaccinations will be administered in the clinic by authorized personnel once AEs have been assessed, vitals have been taken and a symptom-directed PE conducted. Females who have not demonstrated an FSH level >30 mIU/mL must also pass a urine pregnancy test (see [Section 8.3.2](#)).

Participants in Groups 1A and 2A will receive their first vaccination after the 12-hour PK sample in the evening of Day 8, and their second vaccination on Day 23. Site personnel who administer the vaccine should be trained in the early recognition of symptoms of anaphylactic reactions, a rare but potentially serious reaction to parenteral injections.

Sites should be prepared to treat participants experiencing clinically significant dyspnea or hypotension, wheezing or generalized urticarial reactions. Appropriate medical therapy for anaphylaxis should be administered, if indicated, which should include IM or subcutaneous epinephrine 1:1000, and may include corticosteroids, diphenhydramine, bronchodilators, intravenous volume expansion, and/or oxygen. Participants will be evaluated and carefully monitored until complete resolution of any signs and symptoms, should they occur.

If a participant in Groups 1 or 2 has a moderate or severe illness and/or an oral temperature greater than 100.4°F within three days before vaccination 1, or any condition that, in the opinion of the Investigator, would render vaccination unsafe or would interfere with evaluations, these participants will be withdrawn from the study and will be considered ineligible for rescreening. These participants will be instructed to cease taking antibiotics but to continue with their e-diary for an additional 7 days beyond the day they ceased taking antibiotics at which point they will be asked to return to the site and complete the EWV procedures. If the reason for not receiving vaccine is an AE/SAE/AESI, the participants will be followed until the event has resolved, stabilized or the participant has been referred to another physician. These participants, having not received any vaccine, will not be included in the long-term follow-up nor will they have additional blood samples taken for TNA, TSH or autoantibodies.

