Any participant in Group 3 who has a moderate or severe illness and/or an oral temperature greater than 100.4°F within three days before vaccination 1, or any condition that, in the opinion of the Investigator, would render vaccination unsafe or that would interfere with evaluations may be re-screened and re-randomized with the event which precluded vaccination being added to that participant's medical history. If such an event were to occur within three days of vaccination 2, the vaccination must be delayed but should still occur within the 1-day study window. Participants unable to receive vaccination 2 within the allowed study visit window will remain in the study and be followed for safety.

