7.3. Individual Participants

All participants have the right to withdraw at any point during treatment without prejudice. The PI can also discontinue a participant from a trial at any time if medically necessary or for reasons of noncompliance.

Every attempt will be made to follow participants for safety for the entire duration of the trial through the Month 12 safety follow-up providing they have received at least one vaccination. Participants in Groups 1 and 2 who discontinue treatment prematurely for any reason after receiving the first dose of antibiotic but prior to receipt of the first vaccination will be encouraged to return to the clinic for the Early Withdrawal procedures minus the blood draws for autoantibodies, TSH and TNA. Participants who discontinue treatment prematurely for any reason after receiving the first vaccination will be encouraged to continue in the study for any

AV7909 Anthrax Vaccine

IND 014451

Protocol EBS.AVA.210, Version 3.0 (28 October 2019)

remaining study visits (for safety assessments only) and the safety follow-up phone calls at Months 3, 6, 9 and 12 (post-vaccination).

If a participant discontinues treatment and/or involvement in the study, the reason(s) must be fully evaluated and recorded appropriately in source documents and eCRFs. Reason for discontinuation of treatment and reason for withdrawal from the study are to be recorded separately on eCRFs. If the participant is being discontinued because of an AE, that AE will be indicated as the reason for discontinuation and/or study withdrawal.

Randomized participants who withdraw for any reason will not be replaced in this trial.

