10.6. Safety Analysis

All safety data will be presented in the form of tabulations and listings, based on the Safety Population. Data summaries will be tabulated by treatment group (Ciprofloxacin only, AV7909 + ciprofloxacin, Doxycycline only, AV7909 + doxycycline, AV7909 only, and Total, ie, all participants receiving any IP) as specified in [Section 10.3](#). Continuous variables will be summarized using number of participants (n), mean, standard deviation (SD), median, minimum, and maximum. Categorical variables will be summarized by the number (frequency) and percentage in each category. No formal hypotheses testing will be conducted for safety data.

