## 8 SAFETY ANALYSIS

All safety data will be presented in the form of tabulations and listings, based on the Safety Population. Data summaries will be tabulated by treatment group as specified in [Section 3.2](#).

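### The SAP's three safety groups have no place for participants who took an antibiotic but never received AV7909, although the protocol gives them their own columns

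*SAP*

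**What the plan says.** Protocol 10.6 lists the safety columns as "Ciprofloxacin only, AV7909 + ciprofloxacin, Doxycycline only, AV7909 + doxycycline, AV7909 only, and Total, ie, all participants receiving any IP". An antibiotic taker who was never vaccinated has a column of their own.

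SAP 3.2 admits to the Safety Population every randomized participant with "at least one dose of either antibiotic or AV7909. Participants will be included in the IP group (Group 1, 2, and 3", allocated by treatment received. SAP 8 then states: "Data summaries will be tabulated by treatment group as specified in" SAP 3.2. In SAP 2.4, Group 1 is AV7909 + ciprofloxacin, Group 2 is AV7909 + doxycycline and Group 3 is AV7909 only. The SAP has no antibiotic-only group and gives no reason for departing from the protocol.

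Protocol 6.1.4 foresees such participants. Groups 1 and 2 start antibiotic on Day 4 and Day 2, and the first vaccination is on Day 8. Group 1 and 2 participants with a moderate or severe illness or fever in the three days before that vaccination are withdrawn. Of them the section says: "These participants, having not received any vaccine, will not be included in the long-term follow-up". Section 7.3 covers stops for any other reason: those who stop "prior to receipt of the first vaccination will be encouraged to return to the clinic for the Early Withdrawal procedures".

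**The concern.** Safety of co-administration is a secondary objective, and Group 3 is the vaccine-alone reference. A reader will take the Group 1 and Group 2 columns to show what happens when AV7909 is given with an antibiotic. If those columns also contain people who never received AV7909, any percentage whose numerator can come only from vaccinated participants is too low in Groups 1 and 2. Group 3 has no matching dilution, so the comparison could make co-administration look slightly better tolerated than it is.

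The same participants enter the 12-month SAE and AESI denominators although the plan does not schedule them for that follow-up.

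**Working it through.** The plan states no figure on this point, so the check compares the texts and then sizes the effect.

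**1. Where the participant is counted.** Take someone randomized to Group 1 who takes ciprofloxacin from Day 4 and is withdrawn before vaccination on Day 8.
- Safety Population: included, with at least one antibiotic dose (SAP 3.2; Protocol 10.3 agrees).
- Column under Protocol 10.6: ciprofloxacin only.
- Column under SAP 3.2 and 8: of the three groups, only Group 1 contains ciprofloxacin. Allocation by treatment received leads to no other place.

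**2. The counterpart in Group 3.** A Group 3 participant who misses vaccination 1 has received no IP and is not in the Safety Population. Section 6.1.4 adds that such a participant "may be re-screened and re-randomized with the event which precluded vaccination being added" to the medical history. The mixing can occur only in Groups 1 and 2.

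**3. Follow-up.** Section 6.1.4 has participants precluded from vaccination "continue with their e-diary for an additional 7 days beyond the day they ceased taking antibiotics" and then attend the early withdrawal visit. Section 7.3 aims to follow participants to the "Month 12 safety follow-up providing they have received at least one vaccination". The never-vaccinated are therefore not scheduled for the quarterly calls. If an AE was the reason for not vaccinating, 6.1.4 follows it until it resolves, stabilises or is referred.

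**4. Denominator for reactogenicity.** SAP 8.6.1 summarises reactions after each vaccination but states no denominator. Appendix I bases percentages on the column-header N unless otherwise specified. It also allows those present at the visit in by-visit summaries, and a footnoted denominator. The dilution applies only under the header-N default.

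**5. Size.** Let 70 be the planned group size (SAP 2.4), all dosed, with k of them never vaccinated. Let x be the vaccinated participants with a vaccine-specific event.
- Rate among the vaccinated: p = x/(70 − k).
- Tabulated rate: x/70 = p(70 − k)/70.
- Relative fall: k/70. In percentage points: 100 × p × k/70.

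For k = 1 the relative fall is 1/70 = 1.4%. Protocol 2.3.2.3 gives 40% to 90% for the common injection-site reactions. At those rates one participant costs 0.40/70 = 0.6 points and 0.90/70 = 1.3 points.

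| k (assumed) | Relative fall | Tabulated, p = 40% | Tabulated, p = 90% |
|---|---|---|---|
| 0 | 0% | 40.0% | 90.0% |
| 1 | 1.4% | 39.4% | 88.7% |
| 3 | 4.3% | 38.3% | 86.1% |
| 7 | 10.0% | 36.0% | 81.0% |

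Group 3 stays at p throughout.

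**6. Which tables.** The formula applies to reactogenicity (subject to step 4), to TEAEs related to the vaccine (SAP 8.1.3) and to AESIs by relationship to AV7909 (SAP 8.1.5). It does not apply to the all-TEAE tables. SAP 8.1.1 counts any AE from first exposure to any study treatment, so an antibiotic-only participant can add events as well as a denominator.

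**7. The AV7909 Total column.** Protocol 10.6.1 and SAP 8.1.2 both order tables by this column, and neither defines it. The only total defined in 10.6 is everyone who received any IP, which includes the never-vaccinated.

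**The case against.** The SAP nowhere says that it removes columns, and allocation by treatment received could be read as keeping the protocol's layout. Retaining an AV7909 Total column suggests that some columns are not AV7909. This shows that the intention may have been different. It does not supply a category: Protocol 10.3 uses the same allocation rule but feeds five columns, while the SAP offers three groups.

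The SAP also discloses much of what is needed. SAP 5.4.2 tabulates how many received each vaccination, SAP 5.1 reports discontinuations and last visits, and SAP 8.1.3 has a table of TEAEs with onset before the first vaccination. A reader could largely recover k. That makes the problem visible, but it does not correct the percentages. The 8.1.3 table isolates a time period, not the people who were never vaccinated.

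For reactogenicity, the phrasing of SAP 8.6.1 and the per-vaccination diary compliance in SAP 8.6.3 make a recipient denominator a natural reading. That stands. The denominator is unstated, not demonstrably wrong.

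The strongest objection concerns the remedy. Splitting by vaccination received conditions on a post-randomization event, and it would move people who stopped because of early antibiotic AEs out of the co-administration columns. Keeping all treated participants by IP group is a defensible choice for overall TEAEs, so that view should be kept as well.

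**Conclusion.** The mismatch between Protocol 10.6 and SAP 3.2 and 8 is real and should be settled before database lock. It affects descriptive safety percentages only. In vaccine-specific summaries Groups 1 and 2 fall by k/70 relative, 1.4% per never-vaccinated participant, and Group 3 does not move. This rests on a treated group of 70, on k, which the documents do not give, and for reactogenicity on use of the header-N default. With k = 0 nothing changes.

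A reader might infer more in four ways, none of them supported:
- That all safety rates in Groups 1 and 2 are understated. In the all-TEAE tables the direction is open, because antibiotic AEs count.
- That k could be near the planned 25% loss. That allowance covers all exclusions from the immunogenicity analysis, not missed first vaccinations.
- That early leavers' events are lost after the withdrawal visit. An AE that precluded vaccination is followed further.
- That non-serious AEs are collected unequally at the safety calls, because Table 8 footnote s and Table 9 footnote p omit them. Both footnotes cite Section 8.1.7, which requires AEs, and the AE rows of both tables are marked at the calls. The slip is editorial.

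**What to change.** - In SAP 3.2 and 8, restore the Protocol 10.6 columns, with ciprofloxacin only and doxycycline only apart from the AV7909 + antibiotic columns.
- Define AV7909 Total as participants with at least one AV7909 dose.
- In SAP 8.6.1, state that the reactogenicity denominator is recipients of the given vaccination.
- Keep a TEAE summary of all treated participants by IP group alongside, so that early antibiotic AEs stay in view.

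The cost is column and denominator definitions and one additional layout of the TEAE summary. No new visits or data are needed. The drawback is that the split columns are not randomized comparisons, which a table footnote should say. As a separate editorial correction, the two call footnotes can be aligned with Section 8.1.7.

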4.1.1. Group 1A Schedule

The 40 participants in Group 1A will have blood drawn at randomization (Day 1) for TNA testing, and TSH and autoantibody testing. These participants will receive both ciprofloxacin and AV7909 and undergo four ciprofloxacin PK sessions. They will have a final blood draw for TNA on Day 37 and will complete their final visit for safety including a blood draw for TSH and autoantibodies on Day 51. Note: testing of samples for TSH levels and autoantibodies will be performed only if medically indicated (ie, as per PI's discretion based on a report of a potential AESI).

Ciprofloxacin (500 mg by mouth [per os] every 12 hours [q 12 hr]) will be administered intermittently, ie, on Days 4-9, Days 22-24 and Days 31-37. Participants will use the same supply of ciprofloxacin in the clinic and for self-administration at home.

AV7909 (0.5 mL) will be administered by IM injection delivered on:

- Day 8 (Note: this will be administered in the evening following completion of the PK session and administration of the evening antibiotic)
- Day 23

Ciprofloxacin PK sessions will be performed on Days 4, 8, 31, and 35. On days with PK sessions, blood samples for measurement of ciprofloxacin concentrations will be collected at 0.25, 0.5, 0.75, 1, 1.5, 2, 2.5, 3, 4, 5, 6, 8, 10 and 12 hours post-dose (± 5 min through hr 4, then ± 15 min thereafter). Ciprofloxacin pre-dose or trough values (all samples collected prior to the morning dose of ciprofloxacin) will be measured on Days, 4, 5, 6, 7 and 8; and again on Days 31, 32, 33, 34 and 35. The ciprofloxacin pre-dose values on Days 4, 8, 31 and 35 serve as the $t=0$ values for the PK sessions on those days as well as contributing to the two trough value analyses used to evaluate achievement of steady state before and after vaccination.

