Bilirubin (when accompanied by any increase in Liver Function Test) increase by factor	1.1–1.25 x ULN	1.26–1.5 x ULN	1.51–1.75 x ULN	> 1.75 x ULN
Bilirubin (when Liver Function Test is normal) increase by factor	1.1–1.5 x ULN	1.6–2.0 x ULN	2.0–3.0 x ULN	> 3.0 x ULN
Hematology				
Hemoglobin, female (g/dL)	11.0–12.0	9.5–10.9	8.0–9.4	<8.0
Hemoglobin decrease from baseline value, female (g/dL)	Any decrease–1.5	1.6–2.0	2.1–5.0	>5.0
Hemoglobin, male (g/dL)	12.5–13.5	10.5–12.4	8.5–10.4	<8.5
Hemoglobin decrease from baseline value, male (g/dL)	Any decrease–1.5	1.6–2.0	2.1–5.0	>5.0

AV7909 Anthrax Vaccine

IND 014451

Protocol EBS.AVA.210, Version 3.0 (28 October 2019)

Panel and Analyte^a	Mild (Grade 1)	Moderate (Grade 2)	Severe (Grade 3)	Potentially Life Threatening (Grade 4)^b
WBC increase (cell/mm ³)	10,800–15,000	15,001–20,000	20,001–25,000	>25,000
WBC decrease (cell/mm ³)	2,500–3,500	1,500–2,499	1,000–1,499	<1,000
Lymphocyte decrease (cell/mm ³)	750–1,000	500–749	250–499	<250
Neutrophil decrease (cell/mm ³)	1,500–2,000	1,000–1,499	500–999	<500
Eosinophils (cell/mm ³)	650–1,500	1,501–5,000	>5,000	Hypereosinophilic
Platelets decrease (cell/mm ³)	125,000–140,000	100,000–124,000	25,000–99,000	<25,000
Urine				
Protein	Trace	1+	2+	Hospitalization or dialysis
Glucose	Trace	1+	2+	Hospitalization for hyperglycemia
Blood (microscopic) (RBC/hpf)	1–10	11–50	>50 and/or gross blood	Hospitalization or PRBC transfusion

ALT = alanine aminotransferase; AST = aspartate aminotransferase; HPF = high power field; PRBC = packed red blood cells; RBC = red blood cells; ULN = upper limit of normal range; WBC = white blood cell.

^a Laboratory normal reference ranges have not been taken into consideration for the toxicity grading scale.

^b The clinical signs or symptoms associated with laboratory abnormalities might result in characterization of the laboratory abnormalities as Potentially Life Threatening (Grade 4). For example, a low sodium value that falls within a Grade 3 parameter (125-129 mE/L) will be recorded as a Grade 4 hyponatremia event if the participant had a new seizure associated with the low sodium value.

AV7909 Anthrax Vaccine

IND 014451

Protocol EBS.AVA.210, Version 3.0 (28 October 2019)

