### 2.2.2 PK Sampling

Serial PK assessments will be conducted on the following days:

- Group 1A (ciprofloxacin): Days 4, 8, 31, and 35;
- Group 2A (doxycycline): Days 2, 8, 32, and 38.

On these serial PK assessment days, blood samples for measurement of drug concentrations will be collected at 0.25, 0.5, 0.75, 1, 1.5, 2, 2.5, 3, 4, 5, 6, 8, 10, and 12 hours post dose ( $\pm 5$  min through hr 4 then  $\pm 15$  min).

In addition, antibiotic pre-dose or trough values will be measured prior to the antibiotic's morning doses on the following days:

- Group 1A (ciprofloxacin): Days 4, 5, 6, 7, and 8, and on Days 31, 32, 33, 34, and 35;
- Group 2A (doxycycline): Days 2, 3, 4, 5, 6, 7, and 8, and on Days 32, 33, 34, 35, 36, 37, and 38.

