## 2.4 Sample Size and Power Considerations

The sample size for this study was selected based on both the primary and secondary endpoints.

Assessment as to whether vaccination with AV7909 affects the PK of either ciprofloxacin or doxycycline will be made based on the geometric mean of the within-participant ratios (post-vaccination over pre-vaccination) of AUC0-12h and Cmax. The equivalence margin for the geometric mean ratio is [0.80, 1.25], which will be compared with the 90% confidence interval (CI) for the geometric mean of with-participant ratios of AUC0-12h and Cmax. Assuming the coefficient of variation (CV) is 30% for the geometric mean ratio and the true geometric mean ratio is 0.95, 27 participants allow for 90% power to reject the null hypothesis at a significance level of 5%. A group size of 40 participants for Group 1A (AV7909 + ciprofloxacin with PK) or Group 2A (AV7909 + doxycycline with PK) is planned to allow for up to 30% of participants being excluded from the PK Population.

A sample size of 53 in each of the IP groups (Group 1 = AV7909 + ciprofloxacin, Group 2 = AV7909 + doxycycline, and Group 3 = AV7909 only) provides 90% power at 2.5% one-sided significance level for the non-inferiority test, defined as the lower bound of the two-sided 95% CI of the geometric mean ratio of the AV7909 + antibiotic over AV7909 only (Group 1 vs. Group 3, Group 2 vs. Group 3) greater than 0.5. This assumes that the true ratio of the geometric means between two groups is 0.85 and the CV of TNA NF50 values in each group is 100%. A total of 70 per IP group is planned to allow for up to 25% of drop-out rate.

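### Hematology tables pooled by IP group would mix blood loss from PK sampling in Groups 1A and 2A with any antibiotic effect when read against Group 3

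*SAP*

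**What the plan says.** - **Grouping.** SAP 3.2, on the Safety Population: "Participants will be included in the IP group (Group 1, 2, and 3) according to the treatment they received". SAP 8: "Data summaries will be tabulated by treatment group as specified in" Section 3.2. SAP 8.2 then gives hematology change, shifts and highest grade by treatment group. Protocol 10.6 lists the columns: "Data summaries will be tabulated by treatment group (Ciprofloxacin only, AV7909 + ciprofloxacin, Doxycycline only, AV7909 + doxycycline, AV7909 only", plus a total. It has no PK/non-PK split. The table template in SAP Appendix I shows Groups 1, 2 and 3.
- **Terminology.** SAP Table 1 has separate columns for IP Group (1, 2, 3) and Treatment Group (1A, 1B, 2A, 2B, 3), and SAP 3.2 uses the second term for 1A and 2A in the PK Population. So the wording in SAP 8.2 is not free of doubt.
- **PK sampling.** Protocol 4.1.1, for Group 1A: "blood samples for measurement of ciprofloxacin concentrations will be collected at 0.25, 0.5, 0.75, 1, 1.5, 2, 2.5, 3" and on to 12 hours. SAP 2.2.2 gives the same times for both antibiotics. Protocol 8.4 limits this sampling to 1A and 2A.
- **Hematology.** It is taken at Screening and Day 51, or at early withdrawal (Protocol 8.3.2, SAP 2.2.4.2).
- **Grading.** Protocol Table 13 has rows for fall from baseline, for example "Hemoglobin decrease from baseline value, female (g/dL"), in which any decrease up to 1.5 g/dL is Grade 1, 1.6–2.0 is Grade 2 and 2.1–5.0 is Grade 3. Incidence of laboratory abnormalities is a secondary safety endpoint, with no hypothesis test (SAP 2.3.2.1).

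**The concern.** Group 3 is the only group without an antibiotic, so readers will use it to judge the safety of giving antibiotic and vaccine together, which is a secondary objective. The pooled antibiotic arms differ from Group 3 in a second respect: more than half of their participants have a heavy sampling schedule that Group 3 lacks. Repeated phlebotomy lowers hemoglobin, hematocrit and RBC count, and Table 13 grades even a small fall. A spurious red-cell signal would also be easy to believe, because Protocol Table 4 lists anemia among the ciprofloxacin reactions. With no model or test planned for safety, the table layout is the main protection against reading blood loss as a drug effect.

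**Working it through.** **Group sizes (the plan's own figures).** SAP 2.4: "A group size of 40 participants for Group 1A (AV7909 + ciprofloxacin with PK) or Group 2A", and "A total of 70 per IP group is planned to allow for up to 25% of drop-out rate".
- Paired TOST, log-scale SD √ln(1 + 0.30²), true ratio 0.95, n = 27: simulated power 0.906, against 90% stated.
- Two-sample non-inferiority test, SD √ln 2, effect ln(0.85/0.5), n = 53: power 0.902, against 90% stated.
- Inflation: 27/0.70 = 38.6, so 39 (40 planned); 53/0.75 = 70.7, so 71 (70 planned).

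The sizes reproduce to within one participant. The PK share of each antibiotic arm is 40/70 = 0.571; in Group 3 it is 0.

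**Samples per participant.** Each session has 14 post-dose samples (SAP 2.2.2: "0.25, 0.5, 0.75, 1, 1.5, 2, 2.5, 3, 4, 5, 6, 8, 10, and 12 hours post dose"). Protocol 4.1.1 and 4.1.3 use the pre-dose value as both t=0 and trough, so it is counted once.
- 1A: 4 × 14 + 10 pre-dose/trough = 66
- 2A: 4 × 14 + 14 pre-dose/trough = 70
- 1B, 2B, 3: 0

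Averaged over the pooled arm: 66 × 40/70 = 37.7 (ciprofloxacin) and 70 × 40/70 = 40.0 (doxycycline), against 0 in Group 3.

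**Timing.** The last PK session is on Day 35 (1A) or Day 38 (2A), 16 or 13 days before Day 51. All PK sampling lies between the two scheduled hematology samples.

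**Decomposition of mean change.**

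Pooled arm − Group 3 = antibiotic effect + 0.571 × sampling effect

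Pooled columns alone cannot separate the two terms.

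**Illustrative size (assumed inputs).** The documents give no volume per sample, recovery rate or SD of change. At 2–6 mL per sample the total is 2 × 66 = 132 mL to 6 × 70 = 420 mL. With 5 L blood volume, hemoglobin 14 g/dL and recovery r by Day 51, the remaining fall is 14 × V/5000 × (1 − r):
- 132 mL, r = 0.75: 0.09 g/dL in 1A; × 0.571 = 0.05 in the pooled arm
- 280 mL, r = 0: 0.78 g/dL
- 420 mL, r = 0: 1.18 g/dL in 2A; × 0.571 = 0.67 in the pooled arm

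Take a remaining fall of 0.1–0.8 g/dL and an SD of change of 0.5–0.8 g/dL. With results to 0.1 g/dL, the share with any recorded fall is Φ((fall − 0.05)/SD), and the pooled share is 40/70 × PK share + 30/70 × non-PK share. The antibiotic effect is set to zero:

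| Fall | SD | 1A or 2A | No PK sampling (= Group 3) | Pooled arm | Difference (points) |
|---|---|---|---|---|---|
| 0.1 | 0.8 | 0.525 | 0.475 | 0.504 | 2.8 |
| 0.1 | 0.5 | 0.540 | 0.460 | 0.506 | 4.6 |
| 0.8 | 0.8 | 0.826 | 0.475 | 0.675 | 20.0 |
| 0.8 | 0.5 | 0.933 | 0.460 | 0.730 | 27.0 |

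For falls of 1.6 g/dL or more (Grade 2 and above), over the wider range 0.09–1.18 g/dL, the pooled arm has 0.6–15% against 0.5% in Group 3 at SD 0.6, and 3.1–19% against 2.6% at SD 0.8. The upper ends need 6 mL per sample and no recovery.

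**The case against.** The case against has four parts.

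1. **The split comparison is not clean.** A or B membership follows enrolment order: about the first 40 randomised to each antibiotic become 1A or 2A, and later participants become 1B or 2B (Protocol 4.1, SAP 2.5.1). Group 3 spans the whole period. A reader might infer that 1B or 2B against all of Group 3 is the unconfounded comparison. The documents do not support that, because it sets late enrollees against early and late ones together. A and B also differ in dose supervision: self-administered doses are 14/31 in 1A and 29/31 in 1B, 15/35 in 2A and 33/35 in 2B (Protocol synopsis). An A-versus-B difference could therefore reflect adherence or calendar time as well as phlebotomy. This stands, and it shapes the remedy.
2. **The wording may already mean a split.** Given SAP Table 1, treatment group could denote the five subgroups. Pooling is the likelier reading, since SAP 8 points to a section that names IP groups and Protocol 10.6 has no split. The ambiguity is itself a reason to define the columns.
3. **The size is assumed.** This stands; the low end of the range is negligible.
4. **Safety is descriptive, and participant listings show every result and grade.** This stands, so an A/B check could be made afterwards. A display specified in advance is still better than one built after a signal has been seen.

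**Conclusion.** The point holds as a partial confounding of red-cell results in descriptive tables. The 66 and 70 samples, the 40/70 share and the timing follow directly from the documents. The pooling is the most plausible reading, not a certainty. The direction is clear: sampling makes the antibiotic arms look worse. The size could be anything from about 50% against 48% with any fall to 73% against 46%, depending on assumed volume, recovery and SD.

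Three stronger readings should be resisted:
- That sampling makes 57% of each antibiotic arm abnormal. That figure is the share sampled. Under the same model 46–48% of unsampled participants show a fall anyway, so Grade 1 on this row is largely noise.
- That the safety tables as a whole are compromised. The mechanism concerns hemoglobin, hematocrit and RBC count.
- That an error rate is affected. No safety test is planned. A laboratory result is recorded as an adverse event only at Grade 3 or higher or if the investigator judges the change clinically significant (Protocol 8.3.2), so most of the effect would stay in the laboratory tables.

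**What to change.** In SAP 8.2:
- State what the columns are, and keep pooled Groups 1, 2 and 3 as the main, randomised display.
- Add supportive change, shift and maximum-grade displays for hemoglobin, hematocrit and RBC count by 1A, 1B, 2A, 2B and 3. Maximum grade applies only where Table 13 grades the analyte.
- For the comparison free of PK sampling, set 1B and 2B each against Group 3 participants randomised in the same period, that is, after the matching A subgroup was filled. Label it supportive. Randomisation is 1:1:1 in blocks of 3 within site, so roughly 70 − 40 = 30 Group 3 participants should qualify.
- Add a footnote that A and B also differ in calendar time and supervised dosing, so an A-versus-B difference is not attributable to phlebotomy alone.

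The cost is a few extra tables and a date rule for the concurrent Group 3 set. No new data are needed. The drawback is small columns, about 30 each, with correspondingly imprecise percentages.
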